### Additional Analyses

Functionality measures (including measure that will be included in the primary effectiveness endpoint of total clinical failure)

The analysis will include the calculation of the following functionality measures for both condom types. These will be reported as probabilities including 95% confidence intervals.

Nonclinical failure: Number of condoms that could not be used because of breaks,

donning problems, or defect over the number of condoms

opened for use

Clinical breakage: Number of condoms that broke during intercourse over

the number of condoms used for vaginal intercourse (clinical breakage will be included in the primary effectiveness endpoint

of total clinical failure)

Complete slippage Number of condoms that slipped completely (100%) off the

erect penis during intercourse or on correct withdrawal over the number of condoms used for vaginal intercourse. (Condoms that slip completely (100%) off the penis during withdrawal when neither partner held the condom at the base

of the erect penis during withdrawal are excluded.)

Slippage during intercourse: Number of condoms that slipped off penis during intercourse

over the number of condoms used for vaginal intercourse

Slippage during withdrawal: Number of condoms that slipped off penis during withdrawal

over the number of condoms used for vaginal intercourse.

Partial slippage: Number of condoms that slipped off penis during withdrawal

over the number of condoms used for vaginal intercourse.

Total failure: Number of condoms that broke during package opening,

donning, intercourse or correct withdrawal, or slipped off the penis during intercourse or correct withdrawal or could not be used (donning problems or defect) over the number of condoms

opened for use.

Total slippage: Number of condoms that slipped off penis during intercourse or

correct withdrawal over the number of condoms opened for use (total slippage will be included in the primary effectiveness

endpoint of total clinical failure)

Other failure: Number of condoms that could not be used due to donning

problems or defect over the number of condoms opened for use

We will also assess the association between penis size and breakage/slippage for each condom type e.g., whether increased or decreased rates for total clinical failure, clinical breakage and total slippage as a function of penis size.

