# Definition of the primary effectiveness endpoint, total clinical condom failure rate:

The probability of total clinical condom failure is defined as the number of condoms that break or slip completely off the penis during intercourse or correct withdrawal as a proportion of the condoms used for vaginal intercourse.

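### The SAP's functionality list defines partial slippage as withdrawal slippage, and its clinical breakage and total slippage do not match the primary endpoint they are said to feed

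*Combined protocol and SAP*

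**What the plan says.** All of this is in Section VI of the combined protocol and SAP.

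- **Primary endpoint.** Under its own heading, total clinical failure is the "number of condoms that break or slip completely off the penis during intercourse or correct withdrawal", as a proportion of condoms used in vaginal intercourse.
- **Slippage rows (Additional Analyses).** The list gives "Slippage during intercourse: Number of condoms that slipped off penis during intercourse", then "Slippage during withdrawal: Number of condoms that slipped off penis during withdrawal", then "Partial slippage: Number of condoms that slipped off penis during withdrawal". All three are divided by condoms used in vaginal intercourse. A separate complete slippage row requires the condom to come off entirely.
- **Breakage row.** "Clinical breakage: Number of condoms that broke during intercourse over" condoms used in vaginal intercourse. A note says this measure forms part of the primary endpoint.
- **Total failure.** Breaks are counted at package opening, "donning, intercourse or correct withdrawal, or slipped off the penis during intercourse or correct withdrawal", together with unusable condoms, over condoms opened.
- **Nonclinical failure.** "Number of condoms that could not be used because of breaks", or because of donning problems or defects, over condoms opened.
- **Total slippage.** Condoms that slipped off in intercourse or at correct withdrawal, over condoms opened. A note says this too forms part of the primary endpoint.
- **Penis size.** The SAP will examine "whether increased or decreased rates for total clinical failure, clinical breakage and total slippage as a function of penis size".

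**The concern.** Breakage and slippage are named in the study's primary objective (Section I), so readers will look at their separate rates as well as the combined one. Followed literally, the list has three faults.

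1. Two rows always show the same number, and no row shows condoms that moved along the penis without coming off.
2. The breakage row can be lower than the breakage counted inside the endpoint it is said to feed.
3. The slippage measure tied to the endpoint has a different denominator from the endpoint and does not say that the slip must be complete.

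Faults 2 and 3 carry into the penis-size analysis, which uses clinical breakage and total slippage. There is also a practical risk: a programmer who builds the endpoint from the rows marked as belonging to it, instead of from the endpoint's own definition, would drop breaks at correct withdrawal.

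**Working it through.** **1. The plan's own figures.** Section V plans 1,500 potential uses per condom type, and 0.85 × 1,500 = 1,275. The Sample Size Justification states 95% power at that number. Inputs: 255 couples, Z = 5, ρ = 0.2, both failure rates 0.04, margin 0.025, true difference 0.

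- Var = 2 × 0.04 × 0.96 × (1 + 4 × 0.2)/5 − 2 × 0.2 × 0.04 × 0.96 = 0.027648 − 0.015360 = 0.012288.
- Power = Φ(0.025 × √(255/0.012288) − 1.960) = Φ(1.641) = 0.9496.

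The stated 95% reproduces. It rests on total clinical failure alone, so no correction to the component rows changes it.

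**2. Definitions side by side (paraphrased).**

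| Measure | Event counted | Denominator |
|---|---|---|
| Primary endpoint | break or complete slip; intercourse or correct withdrawal | used |
| Clinical breakage | break; intercourse | used |
| Complete slippage | complete slip; intercourse or correct withdrawal | used |
| Slippage during withdrawal | slipped off; withdrawal | used |
| Partial slippage | slipped off; withdrawal | used |
| Total slippage | slipped off; intercourse or correct withdrawal | opened |
| Nonclinical failure | could not be used | opened |
| Total failure | break from opening to correct withdrawal, slip, or unusable | opened |

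*Partial slippage* and *slippage during withdrawal* are identical in both columns, so the two rates are equal for every condom type whatever the data.

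**3. Where a break at correct withdrawal goes.** It is in the primary endpoint. In the endpoint sentence the timing phrase may govern both verbs, or only the slipping. On the second reading breaks have no timing limit, so a break at correct withdrawal counts either way. It is not in clinical breakage as worded. It is not nonclinical failure, because the condom was used. Total failure includes it, but that is a composite.

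**4. Size per event.** Each such break lowers reported clinical breakage by 1/1,275 = 0.078 percentage points. For scale, the 4% planning limit gives 0.04 × 1,275 = 51 failures per condom type, and 1/51 = 2.0%. The documents do not give the share of breaks that occur at withdrawal, and none is assumed here.

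**5. Would a reader notice from the totals?** Let T be total clinical failures, B clinical breakage as worded and S complete slips. Suppose every withdrawal break happens at correct withdrawal. Then

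T − (B + S) = (breaks at correct withdrawal without a complete slip) − (breaks in intercourse with a complete slip).

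The gap can be positive, zero or negative. One event of each kind gives 1 − 1 = 0, although a break has been left out.

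**6. Breaks when the condom was not held.** Exclusion 6 under Observations contributing to the analyses removes only complete slips when the condom was not held at withdrawal. A condom that breaks in that situation stays in the denominator. Whether it counts as a failure depends on which reading of the endpoint sentence in step 3 is taken. The identity in step 5 does not cover this case.

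**7. Total slippage.** With s slips, the row gives s/opened, whereas the endpoint works on s/used. The two differ by the factor used/opened, which the documents do not give. The row also leaves the reader to infer that *slipped off* means completely off.

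**The case against.** The strongest reply is that these are slips of wording in descriptive rows. The partial slippage entry looks like a copied line, and its label, set against complete slippage, shows the contrast intended. Section II, Data Collection, attaches definitions and illustrations to the condom report, and the study says it follows ISO 29943-1:2017. Neither source can be seen here. It would go too far to infer that partial slippage is undefined in practice; what is shown is that the SAP's own definition is wrong.

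A second reply is that intercourse in the breakage row may be meant loosely, as use in contrast to breaks that prevented use. The separate slippage rows by phase count against this, but slippage may be split because holding the condom at withdrawal matters for slipping. So the text does not rule the loose reading out. The literal reading is the more natural one, and the text is inconsistent on either.

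Third, the SAP says the components are included in the endpoint; it does not promise that they add up to it. That stands, so a count of condoms that both broke and slipped is an optional improvement, not a missing commitment.

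Three stronger inferences are tempting. One is that the non-inferiority result is at risk. The documents do not support it, because the endpoint is fully stated under its own heading. Another is that breakage will be materially understated, but nothing in the documents gives the number of withdrawal breaks. The third is that every withdrawal break is a total clinical failure; the endpoint wording reaches clearly only those at correct withdrawal.

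**Conclusion.** The point stands as a correction to descriptive functionality measures that should be made before analysis. Three things are established from the text: partial slippage duplicates withdrawal slippage exactly; clinical breakage, read naturally, omits breaks at correct withdrawal that the endpoint counts; and total slippage does not match the endpoint in denominator or in stated completeness. In the penis-size analysis both the clinical breakage and total slippage parts are therefore out of line with the endpoint, while the total clinical failure part is sound.

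The per-event figure assumes 1,275 evaluable uses and the literal reading of clinical breakage. The total effect is unknown, and would be zero if no condom breaks at correct withdrawal. No conclusion about non-inferiority changes.

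**What to change.** - **Partial slippage:** define it as slipping along, but not completely off, the penis, per condom used in vaginal intercourse, worded to agree with the definitions attached to the condom report.
- **Clinical breakage:** give it the endpoint's break timing (intercourse or correct withdrawal). State in both places whether a break counts when the condom was not held at withdrawal, so that endpoint and component follow one rule.
- **Slippage tied to the endpoint:** move the inclusion note from total slippage to complete slippage. In the penis-size analysis use complete slippage per condom used in vaginal intercourse, or say that total slippage is a separate measure.
- **Optional count:** report condoms that both broke and slipped completely, each counted once in total clinical failure. Once the break rule is shared, breakage + complete slippage − both = total clinical failure.
- **Number of types:** the sentence introducing the list refers to two condom types; it should say all three.

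The cost is SAP wording and at most one added count per condom type. Sample size and primary analysis do not change. According to Data Collection, the condom report records when a problem was noticed, so withdrawal breaks should be identifiable from data already planned. The sponsor should check that the form separates partial from complete slippage.

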## Acceptability measures

Acceptability will be evaluated by comparing physical attributes of the three condom types as well as perceptions about using the product. The following acceptability and preference information will be collected for the three types of condoms:

- a. fit of condom (comfort, lack of movement, lack of constriction)
- b. ease of donning

- c. removing
- d. sensitivity/pleasure (heat transmission, speed of orgasm)
- e. adequacy of lubrication
- f. noise during use
- g. appearance
- h. condom smell/odour
- i. overall preference (liked best/least)
- i. recommend to others
- k. purchase interest/acceptable price

Each partner will rate condom attributes on a scale from 1 to 7. Ordinal acceptability data will be summarized by gender with a mean score for each condom type. Paired t-tests (Alpha= 0.05) will be performed to determine whether the acceptability measures are statistically different. Chi-square tests (Yates correction will be applied when cell sizes contain less than ten events) will be performed for categorical acceptability data. Preference data, including the level of confidence the participants have in the condom type just used, the attribute liked best, the attribute liked least, and their willingness to purchase and recommend the condom type to a friend, will also be summarized.

We will also report genital discomforts and adverse events probably or possibly related to the use of each condom type (see below for definitions of genital discomforts and adverse events).

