#### Data Collection

At the male and female phone screenings (SP-M and SP-F), an initial history will be obtained. The history will elicit information on previous condom use, sexual partners, coital patterns, history of STIs, vaginal infections, and disorders of the reproductive system.

At the first Curbside enrollment visit (E1), couples will be given a penis measurement kit and asked to take measurements of the male's erect penis (length and circumference) prior to use of the first study condom.

At every follow-up Curbside exchange (E2, E3, and E4), each couple will be asked to return a completed condom report for each use of a study condom within 30 minutes after ejaculation. These reports will elicit information on the conditions of use (who put on condom, use of lubrication, duration of vaginal intercourse, positions used during intercourse), subjective impression (ease of donning, fit, quality of lubrication), whether the condom was held at the base of the erect penis during withdrawal, and problems encountered (breakage, slippage, discomfort, lack of lubrication), circumstances of problems encountered (e.g. when noticed, duration). Written instructions and definitions/illustrations of potential condom problems such as breakage and slippage will be attached to the condom report forms.

After completing each set of five condoms, partners will complete acceptability questionnaires regarding their overall experience with each type of condom and return the questionnaires at the next follow-up Curbside exchange (E2, E3, and E4). These self-administered questionnaires, completed independently by both partners, will elicit perceived advantages, disadvantages, problems, and physical reactions related to condom use.

At the fourth and final Curbside exchange (E4), each partner will return a completed comparison form that elicits preferences between the two types of test polyurethane male condoms regarding sensation, comfort, lubrication, fit, ease of use, overall preference, etc.

Data coding, editing, and key entry will be performed at Essential Access Health. Entrypoint Plus software will be used to structure and maintain data files. Raw data from this study will be made available to the Sponsor as MS Excel files.

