# V. Study Design

This study is a masked (investigators, research staff), three-arm crossover, randomized to sequence of use study designed to evaluate the functional performance (breakage, slippage) of two test polyurethane male condoms (.024mm/58mm/190mm – SAGCS-A, .018mm/55mm/170mm – SAGCS-B) each compared to a commercial natural latex condom. (.055mm/53mm/195mm - Trojan Thintensity $^{TM}$  – SAGCS-C). All three study condoms are lubricated with a silicone lubricant. Three hundred (300) couples will be enrolled and asked to use five condoms of each of the study condom type to yield a potential sample size of 1,500 uses for each type of lubricated condom. To minimize a potential learning effect, couples will be randomly assigned to one of six possible sequences of use of the study condoms:

- SAGCS-A SAGCS-B SAGCS-C
- SAGCS-A SAGCS-C SAGCS-B
- SAGCS-B SAGCS-A SAGCS-C
- SAGCS-B SAGCS-C SAGCS-A
- SAGCS-C SAGCS-A SAGCS-B
- SAGCS-C SAGCS-B SAGCS-A

From experience with previous condom breakage/slippage studies, we estimate that at least 85% of couples will complete all 15 condom uses to obtain an actual sample size of approximately 1,275 for each condom type.

The primary effectiveness endpoint of the study is to confirm noninferiority with respect to total clinical failure rates (combined breakage and slippage) of the two test male condoms independently against the control natural rubber latex male condom. As specified in ISO 23409:2011 a noninferiority margin,  $\delta$ , of 2.5% will be used.

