<sup>3 Taylor and Dominik. Noninferiority testing and crossover trials with correlated binary outcomes and small event proportions with applications for the analysis of condom failure data, J Biopharm Statistics, 9 (2) 365 – 377 (1999)

failure probabilities use fewer condoms of either condom type) will be explored to the extent possible in sensitivity analyses. We will also assess the reasons for missing data by condom type in order to examine the assumption of randomness of missing data.

The power calculation used to determine the sample size is based on the assumption that 85% of condom uses will meet the inclusion criteria (1,275 condom uses). The 85% assumption is based on past experience of running studies of this nature. The use of a high initial power target of 95% for the calculations provides a significant level of protection against the consequences of higher than expected discontinuation rates with resulting loss of missing primary effectiveness data. If the completion rate drops to 75%, power will still exceed 90%. Even if the completion rate drops to a low as 60% the power to conclude noninferiority will remain marginally higher than 80%.

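### Categorical acceptability answers are repeated on the same person, but the chi-square test named for them reads as an unpaired test

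*Combined protocol and SAP*

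**What the plan says.** The study is a three-arm crossover in which couples are "asked to use five condoms of each of the study condom type" (Section V, Study Design). After each set of five condoms the partners fill in acceptability questionnaires "regarding their overall experience with each type of condom", and these are "completed independently by both partners" (Section II, Data Collection). Each person therefore gives up to three sets of answers, one per condom type.

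Section VI, Acceptability measures, sets out the analysis in three consecutive statements:

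- The categorical items, which come last of the three, get this rule: "Chi-square tests (Yates correction will be applied when cell sizes contain less than ten events) will be performed for categorical acceptability data".
- The 1 to 7 ratings, treated just before that, are tested as pairs: "Paired t-tests (Alpha= 0.05) will be performed to determine whether the acceptability measures are statistically different".
- The summary of those same ratings, which opens the set, is split between men and women: "Ordinal acceptability data will be summarized by gender with a mean score for each condom type".

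No McNemar, Cochran's Q, GEE or other repeated-measures method is named for the categorical acceptability data anywhere in the document. GEE is specified only for the primary failure endpoint, under Statistical Objectives.

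**The concern.** Pairing is stated for the ratings and dropped in the next sentence for the categorical items, although both come from the same people in the same crossover. The Yates rule is triggered by small cell counts. That is how one describes an ordinary two-by-two table of condom type against answer, in which the same person appears once in each row. Such a test assumes independent rows.

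The grouping by gender is attached only to the ordinal summary. For categorical items it is therefore also open whether men and women are analysed separately or the two partners of a couple are pooled, which would add a second dependence.

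At stake are the p-values for categorical comparisons of polyurethane with latex. The Introduction makes acceptability part of the study objective, and the final report is to include test results. On the by-gender reading with positive correlation, real differences may be missed. With pooled partners, false differences may also be declared too often.

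**Working it through.** **Inputs from the document.** 300 couples; "at least 85% of couples will complete all 15 condom uses" (Section V), which gives 0.85 × 300 = 255; lower completion scenarios of 75% (225) and 60% (180) under Statistical Objectives; alpha 0.05, stated for the t-tests and taken here as two-sided for the chi-square as well. The 85% is a couple-completion rate, not a questionnaire return rate, so it serves only to set a range of respondents per gender.

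**Inputs assumed.** Within-person correlation r between answers about two condom types, from 0 to 0.5, and a binary item with 60% versus 70% saying yes. The only correlation in the plan, 0.2, concerns condom failure. The plan states no power or error figure for the acceptability tests, so there is none to reproduce.

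**Size, two types, by gender.** With equal yes-rates π, the unpaired test takes the variance of the difference as 2π(1−π)/n. The true variance is 2π(1−π)(1−r)/n, so the ratio is 1−r. True size = 2 × [1 − Φ(1.96/√(1−r))].

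**Size, three types in one 3×2 test, equal r.** P(χ²₂ > 5.991/(1−r)) = exp[−5.991/(2(1−r))].

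| r | Two types | Three types |
|---|---|---|
| 0 | 5.0% | 5.0% |
| 0.1 | 3.9% | 3.6% |
| 0.3 | 1.9% | 1.4% |
| 0.5 | 0.6% | 0.25% |

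Simulation of the two-type test (400,000 runs, n = 255, 65% yes) gave 4.9%, 3.8%, 1.9% and 0.6%; McNemar stayed at 4.9% to 5.0%. When yes-rates are low enough for the Yates rule to apply (3%, n = 255), simulated size was 2.6% at r = 0, 1.3% at r = 0.2 and 0.5% at r = 0.4.

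**Power, 60% versus 70%.** The discordant share is ψ = 0.24 + 0.21 − 2r√(0.24 × 0.21) + 0.01. At r = 0.3 this is 0.325, and the true standard error is √((ψ − 0.01)/n).

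- Unpaired: Φ{[0.10 − 1.96√(2 × 0.65 × 0.35/n)]/√((ψ − 0.01)/n)}. At n = 255: (0.10 − 0.0828)/0.0352 = 0.489, power 68.8%.
- McNemar: Φ{[0.10 − 1.96√(ψ/n)]/√((ψ − 0.01)/n)}. At n = 255: (0.10 − 0.0700)/0.0352 = 0.853, power 80.3%.

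| n | r | Unpaired | McNemar |
|---|---|---|---|
| 255 | 0.1 | 66.7% | 70.0% |
| 255 | 0.3 | 68.8% | 80.3% |
| 255 | 0.5 | 71.9% | 91.3% |
| 300 | 0.3 | 76.7% | 86.3% |
| 225 | 0.3 | 62.4% | 75.2% |
| 180 | 0.3 | 51.4% | 65.5% |

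**Same margins, different answer.** With n = 255 and 58% versus 50%, the unpaired statistic is 0.08²/(2 × 0.54 × 0.46/255) = 3.285, p = 0.070, whatever the pairing. McNemar gives p = 0.044 at r = 0.2, 0.020 at r = 0.4 and 0.005 at r = 0.6.

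**Partners pooled.** Let p be the correlation between partners for the same type and c that between partners for different types. The variance ratio becomes 1 + p − r − c, so the test is anti-conservative when p > r + c.

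| p | r | c | Ratio | Size |
|---|---|---|---|---|
| 0.3 | 0.5 | 0.2 | 0.60 | 1.1% |
| 0.3 | 0.3 | 0.1 | 0.90 | 3.9% |
| 0.5 | 0.1 | 0.05 | 1.35 | 9.2% |

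**The case against.** The strongest reply is that the sentence is incomplete rather than wrong. McNemar's test is a chi-square test, often with a continuity correction, and the preceding sentence shows that the authors saw the pairing. This stands as far as intent goes, but the text does not say so, and two analysts could report different p-values from the same data.

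Second, no affected item is named. Attributes are rated 1 to 7 and go to paired t-tests. Several natural categorical items, such as the best-liked attribute or willingness to buy, are listed as preference data to be summarised, with no test attached. The comparison form takes one preference answer per person, for which a one-sample chi-square is valid. The affected set may therefore be small. It need not be empty: the plan commits to testing categorical acceptability data, and purchase interest and recommendation are among the items collected for all three types.

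Third, the correlation and rates are assumed, and nothing says partners will be pooled. Both points are correct. At r = 0.1 with 255 respondents the loss is only about 3 points of power. The 9.2% size needs a partner correlation well above the within-person one; it shows a possible direction of error, not an expected one.

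Fourth, study success rests only on the non-inferiority endpoint, which is analysed by GEE. That is true and limits the importance of the point.

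**Conclusion.** The concern holds on the plain reading of the sentence. The test named for categorical acceptability data does not fit a design in which the same person answers for every condom type.

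By gender, the effect runs from none at r = 0 to a true size of 0.6% at r = 0.5. At r = 0.3, about 9 to 14 points of power are lost on the illustrative item over 180 to 300 respondents. These sizes rest on assumed correlations and response rates, and the direction is fixed only if partners are not pooled. Confidence is medium because a paired test may have been intended.

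The additional acceptability analyses should be corrected. The primary non-inferiority conclusion is untouched.

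**What to change.** Replace the chi-square sentence under Acceptability measures with text that does the following:

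- For categorical items answered once per condom type, specify a paired analysis by gender: McNemar for binary test-versus-control comparisons, in exact form when discordant pairs are few; Cochran's Q for a binary item across all three types; GEE clustered on person for items with more than two categories.
- State whether the partners are analysed separately. If they are pooled, cluster on couple.
- For items answered once per person, such as the comparison form, specify a one-sample test.
- List which categorical items are tested and which are only summarised.

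The cost is SAP wording only, with no added couples, visits or data.

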# X. Adverse Event Management

Subjects will be instructed to contact research staff immediately if they encounter any problems related to the study or any major medical problem. For this study, an Adverse Event (AE) Form is completed for any of the following: 1) genitourinary discomfort reported on a condom report that lasts more than an hour, 2) a non-genitourinary medical problem that might be related to condom use, 3) a new genitourinary condition that starts after use of a study condom, or 4) a serious adverse event. AE Forms are not completed for discomfort/problems that are reported on the condom report and last for less than an hour. A serious adverse event is defined as an adverse experience or concomitant illness that results in death, life-threatening situation, permanent disability, hospitalization, or congenital anomaly. An unanticipated event is defined as one that is not identified in nature, severity, or frequency in the protocol or human safety assessment.

The Principal Investigator (PI) will promptly notify the sponsor by telephone or email of any serious adverse event whether or not related to use of the study condom, or of any unanticipated event that is possibly related to use of the study condom. Also, the PI will notify the Essential Access IRB of any such event as required by IRB policies.

A clinical examination will be arranged for any subject who reports a persistent adverse reaction (irritation, rash, burning, etc.) which arises during his/her study participation if the adverse reaction has not resolved prior to the report. In an acute medical situation, the randomization code will be broken if the PI deems this essential for medical management of the subject. The PI will notify the sponsor as soon as possible, preferably before breaking the code. If the code is broken, the time and reason will be documented for study record and a copy sent to the sponsor.

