## XII. Additional Records and Reports

A final report will be prepared after data collection and analysis is complete. The report will contain tables that present descriptive statistics on the study population, study outcomes, and acceptability measures. Results of statistical tests will be included where appropriate. Narrative descriptions of all results and methods of analysis also will be included.

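### The plan limits adverse events reported by condom type to those judged probably or possibly related, so recorded events judged unrelated have no planned place in that reporting

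*Combined protocol and SAP*

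**What the plan says.** **Reporting.** The rule is the last sentence of Acceptability measures in Section VI: "We will also report genital discomforts and adverse events probably or possibly related to the use of each condom type". It adds a pointer, "see below for definitions of genital discomforts and adverse events".

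**Collection.** Section X lists four triggers for an AE Form:
- "genitourinary discomfort reported on a condom report that lasts more than an hour"
- "a non-genitourinary medical problem that might be related to condom use"
- "a new genitourinary condition that starts after use of a study condom"
- a serious adverse event

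Discomfort that lasts less than an hour stays on the condom report, without an AE Form.

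**Notification.** Under Section X the principal investigator must tell the sponsor of "any serious adverse event whether or not related to use of the study condom".

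**Final report.** Section XII states: "The report will contain tables that present descriptive statistics on the study population, study outcomes, and acceptability measures". It also promises a narrative account of all results.

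**Other summary text.** Baseline and Other Summary Data (Section VI) presents, by condom type, other events and details associated with use of the study condoms. It does not name adverse events.

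**The concern.** The reporting rule is narrower than the collection rule. An event can be recorded on an AE Form, be judged unrelated, and then have no place in any summary by condom type that the plan names.

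Couples use all three condom types in a randomised order, so the type in use when an event begins is set largely by design. Describing events by type makes use of that. Filtering first on a case-by-case causality judgement puts an opinion between the randomisation and the table.

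That judgement is difficult in this trial. Couples receive a separate lubricant at enrolment, and Potential Risks in Section VII attributes the expected irritation, rash and itching to the condom and the lubricant together. An irritation put down to the lubricant could be rated unrelated to the condom and leave the table, even if such irritations clustered on one type.

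What is at stake is how complete the tolerability description is for two new polyurethane condoms. The Introduction presents polyurethane as free of latex allergy, so this description is of direct interest.

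**Working it through.** No arithmetic applies. The plan states no adverse-event rate, safety hypothesis or safety test, so there is no figure to reproduce. The check compares what Section X collects with what the sentence in Section VI reports.

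| Event | Relatedness needed to be recorded? | Place in reporting by condom type if judged unrelated |
|---|---|---|
| Genitourinary discomfort over an hour | No (AE Form) | Depends on whether the qualifier covers genital discomforts |
| New genitourinary condition after use | No (AE Form) | None stated |
| Serious adverse event | No (AE Form) | None stated; still notified to the sponsor |
| Non-serious, non-genitourinary problem | Yes; recorded only if it might be related | Not collected, so nothing to report |
| Discomfort under an hour | No (condom report only) | Depends on whether the qualifier covers genital discomforts |

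**Step 1: how far the qualifier reaches.** In the reporting sentence, the relatedness phrase can attach to adverse events alone or to genital discomforts as well. On the first reading all genital discomforts are reported by type. On the second they are filtered too. New genitourinary conditions that are not discomforts, and SAEs, are filtered on both readings.

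**Step 2: whether other text restores the missing events.** Baseline and Other Summary Data neither names adverse events nor says that its events are included regardless of cause. Section XII names tables on the population, outcomes and acceptability. Neither commits to an adverse-event table covering all causes. Notification to the sponsor is individual case reporting and produces no summary by condom type.

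**Step 3: whether the filter is defined.** The documents give no relatedness scale and name no assessor. Section X does follow the pointer to definitions. It supplies the AE Form triggers, the one-hour threshold, and definitions of serious and unanticipated events. It does not define genital discomfort separately or set out relatedness categories. Two analysts could therefore build different tables from the same records.

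**Step 4: what a change of reporting can reach.** Every row except the fourth concerns events already recorded. A new reporting rule can bring those in. It cannot bring in unrelated events of the fourth kind, because no form is completed for them.

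**The case against.** **The sentence may not be the whole safety report.** Condom reports ask about discomfort, and the acceptability questionnaires ask about physical reactions. Section XII's outcome tables and narrative could include adverse events. This stands in part: that the report is limited to related events is inferred from the absence of any other adverse-event reporting sentence. But none of this text commits to events of all causes by condom type.

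**The filter may not touch genital discomforts.** This stands as a possible reading. If it is the intended one, the most expected reactions are reported in full and the gap is smaller. The wording should settle it.

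**Staff are masked.** Study Design and Section IX say that investigators and research staff do not know the assignment. A reader might infer that the filter would be applied more heavily to test-condom events and so hide a real difference. The documents do not support that, because it would need differential rating, and masking makes this less likely. An even-handed filter still discards recorded events and so loses information.

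**Oversight is intact.** This stands. SAEs are notified to the sponsor regardless of cause, and the sponsor receives the raw data. Unrelated events are missing from a planned tabulation, not concealed from the sponsor.

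**Events judged definitely related.** A reader might infer that these are excluded as well, since the sentence names only two levels. The documents give no causality scale, so no such category is shown to exist. This is at most a drafting gap.

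**Attribution to a type is not perfect.** Other intercourse is permitted during the study, and an event may begin between two sets of condoms. This stands as a reason to state an assignment rule. The existing sentence, which already reports by condom type, needs the same rule.

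**Conclusion.** The concern holds in a limited form. As written, the plan collects genitourinary discomfort over an hour, new genitourinary conditions and SAEs regardless of relatedness. It then reports adverse events by condom type only when they are judged probably or possibly related. Recorded events judged unrelated have no planned place in that description.

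The size cannot be given as a number, because the documents state neither an expected event rate nor the share likely to be judged unrelated. The loss is to descriptive reporting. No safety test is planned, and the primary non-inferiority analysis does not depend on it.

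The conclusion rests on two points: no other text in the documents commits to reporting events of all causes by condom type, and the sentence is followed as written. It does not depend on how the qualifier applies to genital discomforts, which affects only how much is lost. The change should be made, since the gap is clear and cheap to close.

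**What to change.** Replace the reporting sentence in Acceptability measures with a rule that:

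- tabulates all events on AE Forms, all SAEs, and all genital discomforts on condom reports or questionnaires, by condom type in use at onset and by gender, regardless of relatedness;
- gives participants affected over participants exposed to that type, and events over uses of that type;
- shows relatedness as a further column with every category listed, rated by staff masked to condom type, and does not use it as a filter;
- defines genital discomfort, and states how an event that begins between two sets of condoms is assigned.

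Add this table to the list in Section XII.

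The cost is SAP wording and one more table. No change to sample size or procedures is needed. The AE Form itself is not shown, so it is an assumption that it carries an onset date and a relatedness rating; the existing sentence already presupposes an assignment to type and a rating. The downside is that event counts may look less favourable. The change does not recover non-serious, non-genitourinary events thought unrelated, and the report should say that these were not collected.
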